The study comprises two linked, complementary randomized trials. Trial 1, a large pragmatic trial, compares usual care with the clinician-facing Jumpstart for hospitalized older adults with serious illness (target n=2000; ADRD subset, target n=400). Trial 2, a comparative effectiveness trial is a three-arm trial that compares the clinician-facing Jumpstart, the bi-directional, patient-specific Jumpstart and usual care (n=600). Subjects are enrolled from the UW Medicine hospitals (Harborview Medical Center, UW Medical Center - Montlake, UW Medical Center – Northwest). For Trial 1, eligible patients are ≥ 55 years, admitted for a minimum of 12 and a maximum of 96 hours prior to study enrollment to inpatient services, without a documented GOCD during admission, and meet criteria for serious illness; hospitalized patients >80 years are also eligible. For Trial 2, eligible patients meet the same criteria and, in addition, must be sufficiently fluent in English to complete questionnaires and not be under COVID precautions to allow in-person recruitment. For Trial 2, eligible family may include any of the following: legal guardians, durable power of attorney for healthcare, spouses, adult children, parents, siblings, domestic partners, other relatives, and friends. In addition, we will conduct qualitative interviews with key stakeholders including patients/families (n=40, subgroup of patients enrolled for Trial 2) and clinicians (n=50 across Trial 1 and Trial 2).

2) Specific Aims:

Specific Aim 1 (Trial 1): Evaluate the effectiveness of a novel clinician-facing Jumpstart, compared with usual care, for improving the quality of care; the primary outcome is EHR documentation of a goals-of-care discussion during the 30 days after enrollment. Secondary outcomes focus on intensity of care: ICU use, ICU and hospital free days, costs of care during the hospitalization, and 7- and 30-day hospital readmission.

Specific Aim 2 (Trial 2): Evaluate the efficacy of the bi-directional, patient-specific Jumpstart compared to the clinician-facing Jumpstart and usual care for improving quality of care; the primary outcome is EHR documentation of a goals-of-care discussion 30 days after enrollment. Secondary outcomes include: intensity of care outcomes from Aim 1 and patient- and family-reported outcomes assessed by surveys at 3-5 days and

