e) Sampling patients with ADRD

Given the dramatically increasing prevalence of ADRD in the US and the rising intensity of care among these patients,^{11,13} it is particularly important that we understand the effect of interventions to improve quality of palliative care in this group. We designed both trials to be powered to examine heterogeneity of treatment effects (HTE) in this important group. For Trial 1, we will plan to continue recruitment to enhance power in this subgroup. For Trial 2, we will prioritize recruitment of patients with ADRD to maximize this subgroup sample size. We hypothesize that the interventions will be equally effective in this population, but that the proportion of patients with decisional capacity will be lower (enrolling more family members). However, we believe it is important to explicitly examine this hypothesis given the unique features of intensity of care at the end of life for this important and increasing population.

f) Randomization

Patients are randomized in a 1:1 ratio in Trial 1 and 1:1:1 ratio in Trial 2 using variable size blocks and stratified for hospital and ADRD vs. no ADRD. Participating family members or legal surrogate decision makers are assigned to the same arm as the corresponding patient.

g) Intervention

Clinician-facing Jumpstart: First, we use automated methods to examine inpatient and outpatient EHR notes prior to the current admission, identifying current code status as well as all prior POLST forms and advance directives; this information is included on Jumpstart Guides to inform discussions. Second, we deliver the Jumpstart Guide to the primary hospital team (all attending and resident physicians and advanced practice providers) via secure email and either a page (Trial 1) or Epic SecureChat message (Trial 2) alerting the physicians to the presence of the Jumpstart Guide in their email, with the addition of in-person delivery of a paper version in Trial 2 only.

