Additional outcomes for both trials, obtained from the EHR, include utilization metrics associated with intensity of care (i.e., any ICU admissions, any ED visits, any palliative care consultations, and ICU- and hospital-free days); these outcomes will be assessed at 30 and 90 days after randomization. ICU- and hospital-free days are defined as the number of days alive and outside of the ICU (or hospital) within the specified time period after randomization (i.e. 30 days or 90 days).^{22,23} We will also examine the following outcomes: 1) time to first goals-of-care discussion during the 30 days after randomization; 2) occurrence of any hospital readmissions within 7 and 30 days after discharge from the index hospitalization; and 3) mortality status at 90 days and 1 year after randomization. Costs of care during hospital admission and 30- and 90-days following randomization will be obtained from institutional billing systems. Washington State death certificate data will be used to examine mortality after hospital discharge (Table 1).

b) Outcomes derived from patient- and family-reports (Trial 2 only):

Additional outcomes for Trial 2 will be obtained from patient or family surveys. Surveys will be completed targeting three time points: 1) baseline; 2) 3-5 days after randomization; and 3) 4-8 weeks after randomization. Surveys may be completed in person, online, by mail, or by phone, based on respondents' preferences.

Occurrence and quality of discussions: We use previously validated items to assess the occurrence and quality of goals-of-care communication during the hospitalization after randomization.^{9,24-30} Communication occurrence is assessed with a single item.^{9,25} Quality of goals-of-care communication is assessed with the end-of-life communication scale (QOC_eol) of the Quality of Communication (QOC) survey, developed from qualitative interviews and focus groups with a diverse group of patients, families, and clinicians.^{24,26,28}

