This project requires the creation, maintenance, and analysis of a database that includes a variety of measures from multiple sources. This study, like all studies, depends on the quality of the data and therefore systematic data collection, quality control, and data-management procedures will be implemented: 1) protocols for data collection; 2) rigorous training, certification, and periodic re-training of study staff, with ongoing monitoring of adherence to protocols; 3) regular review of questionnaire response rates, respondent burden,⁶⁷ and missing items to identify and correct problems; 4) verification of all data through custom-designed data entry systems; and 5) weekly team meetings to provide feedback to study staff to ensure problems are resolved quickly. To ensure reliability and validity of data, we will use our current methods for training and quality control.⁶⁸⁻⁷² Staff conducting EHR review will undergo the following training: instruction on the protocol, guided practice abstraction, and independent abstraction with reconciliation by a trainer.

9) Protocol modifications

1. Changes to inclusion/exclusion criteria for Trials 1 and 2 (except where noted)
 - a. Lowering the inclusion criteria age from ≥ 65 to ≥ 55 years
 - b. Removing "English speaking" as an inclusion criterion (Trial 1 only)
 - c. Adding hospital admission for a minimum of 12 hours as an inclusion criterion

- d. Removing markers of frailty as an eligibility criterion
 - e. Adding pregnancy, suicide attempt and same-day discharge as exclusion criteria
 - f. Adding COVID-19 as a specific inclusion diagnosis (Trial 1 only)
2. Study design
 - a. For Trial 2, in addition to comparing the bi-directional (survey-based) Jumpstart Guide to the clinician-facing (EHR-based) Jumpstart guide, we will also include a third arm in which patients receive usual care.
 - b. We have increased the target sample size from n=400 to n=600 to accommodate the addition of a third “usual care” arm to the study.
 - c. We have modified the questionnaires that patients receive at baseline such that only patients in the bi-directional Jumpstart arm are presented with items that are used to create the bi-directional (survey-based) Jumpstart Guide. These items are an integral part of the bi-directional intervention and therefore not appropriate for the other arms to complete.
 3. Procedures

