## General characteristics of analysis:

- The predictor of interest in all regression models will be the randomization group: 0=control, 1=intervention.
- Regression models will be automatically adjusted for hospital site and ADRD status (as defined at the time of randomization). There will be no other covariates in the models.
- For Cox models, we will use Stata's "exactp" method for correcting for ties unless there are problems with that method, in which case we will use the Efron method. (See page 4.)

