## Secondary outcomes:

- Timing of goals-of-care discussion during the 30 days after randomization.  
Cox proportional hazards model:  
Outcome coded as for the primary analysis.  
Time = observation time (elapsed days between randomization and whichever came first: observed discussion, death, 30 days after randomization). Censored if outcome=0.
- Mortality at several time points:  
Outcome = death (0=alive at date of mortality status evaluation, 1=died by date of mortality status evaluation)  
TIME POINT #1: death outcome measured from EHR data for the 30 days after randomization.  
TIME POINT #2: death outcome measured from EHR data at time of index hospitalization discharge. (All patients have been discharged from their index hospitalization.)  
TIME POINT #3: death outcome measured from EHR data pulled for analyses on 2/7/22.  
TIME POINT #4: death outcome measured from death certificates covering the year after randomization.  
(a) Linear regression with robust standard errors (logistic regression as additional analysis in case reviewers request it).  
(b) Cox proportional hazards model of time to death.  
The time variable will represent the elapsed days between randomization and whichever came first: death or the date on which mortality status is assessed. Censored if death = 0.
- EHR documentation of whether patient received any ICU care in the 30 days (and also in the 90 days) after randomization  
Linear regression with robust standard errors (logistic regression as additional analysis in case reviewers request it): outcome = 0 if no documentation of ICU care during period of interest; 1 if ICU care occurred during that period
- EHR documentation of whether patient had any ED visits in the 30 days (and also in the 90 days) after randomization  
Linear regression with robust standard errors (logistic regression as additional analysis in case reviewers request it): outcome = 0 if no documentation of ED visits during period of interest; 1 if ED visits occurred during that period

- EHR documentation of any palliative care consultation in the 30 days (and also in the 90 days) after randomization  
Linear regression with robust standard errors (logistic regression as additional analysis in case reviewers request it): outcome = 0 if no documentation of palliative care consultation during period of interest; 1 if PC consultation documented during that period

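### The ICU-care models leave out whether the patient was already in the ICU at randomization, which costs precision on an Aim 1 secondary outcome but causes no bias

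*SAP*

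**What the plan says.** - **Outcome.** The SAP, under Secondary outcomes, lists "EHR documentation of whether patient received any ICU care in the 30 days (and also in the 90 days) after randomization" and codes it as "outcome = 0 if no documentation of ICU care during period of interest; 1 if ICU care occurred during that period". A new admission is not required, and a stay already under way is not separated out.
- **Model.** Linear regression with robust standard errors, with logistic regression in reserve. Under General characteristics of analysis, the SAP adjusts every regression for hospital site and ADRD status and adds: "There will be no other covariates in the models". The SAP's Additional analyses bring in an ADRD interaction and ADRD subgroups. None uses ICU location.
- **Who is enrolled.** The protocol's overview describes Trial 1 patients as "admitted for a minimum of 12 and a maximum of 96 hours prior to study enrollment to inpatient services". That text and section 4c state no ICU exclusion. The exclusions added in section 9 are: "Adding pregnancy, suicide attempt and same-day discharge as exclusion criteria".
- **Randomization.** Protocol section 4f: "stratified for hospital and ADRD vs. no ADRD".
- **Name of the outcome in the protocol.** Section 5a lists "any ICU admissions, any ED visits, any palliative care consultations, and ICU- and hospital-free days". Aim 1 and Table 1 speak of ICU use instead.

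**The concern.** A patient who is in the ICU at randomization and remains there afterwards has the outcome by definition, whatever the Jumpstart Guide does. These patients add a block of 1s to both arms. Baseline ICU status then predicts the outcome almost perfectly, yet the model may not use it, so its variance stays in the residual.

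ICU use is a named intensity-of-care outcome for Aim 1. If the avoidable noise is large, a real reduction in ICU use among patients who can still avoid the ICU could be missed, and a null result would say little. The information needed to remove the noise is already in hand, because the SAP builds ICU-free days from ICU admission and discharge dates.

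**Working it through.** **No figure to reproduce.** Protocol section 7a sizes the trial on the primary outcome only. Neither document gives a rate, effect or power for ICU care.

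**Inputs from the documents.** 1000 patients per arm, two-sided 0.05 (section 7a). Beds (section 4b): ICU 75 + 94 + 15 = 184; acute care 529 + 413 + 218 = 1160. Taking the two counts as separate, ICU beds are 184/1344 = 14% of the total. That describes capacity and is only a rough guide to who is enrolled.

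**Assumed inputs.** f = share in the ICU at randomization, 5-25%. q = later ICU use among the others, 8-25%. Patients in the ICU at randomization all score 1.

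**Step 1: variance with and without the covariate (same q in both arms).**
- Overall rate: p = f + (1 - f)q.
- Variance without baseline ICU status: p(1 - p).
- Variance within baseline strata: (1 - f)q(1 - q), because the ICU stratum contributes none.
- Since 1 - p = (1 - f)(1 - q), the variance ratio reduces to q/p.

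At f = 0.15 and q = 0.10: p = 0.15 + 0.085 = 0.235. Unadjusted variance is 0.235 × 0.765 = 0.1798, and within-stratum variance is 0.85 × 0.09 = 0.0765. The ratio is 0.426 and the SE ratio is √0.426 = 0.652, a 35% reduction. That is worth 1/0.426 = 2.35 times the patients.

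SE reduction over the assumed range:

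| f | q = 8% | q = 10% | q = 15% | q = 25% |
|---|---|---|---|---|
| 5% | 20% | 17% | 12% | 7% |
| 10% | 32% | 27% | 20% | 12% |
| 15% | 39% | 35% | 26% | 17% |
| 25% | 49% | 45% | 36% | 24% |

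The corners are √(0.25/0.2875) = 0.933 and √(0.08/0.31) = 0.508. The ratio q/p falls as f rises and rises with q, so these corners bound the range.

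**Step 2: what this means for power.** Take an assumed 4-point reduction among patients not in the ICU at randomization, with 1000 per arm. At f = 20% and 10% vs 6% among the others:
- Observed rates are 0.20 + 0.80 × 0.10 = 0.280 and 0.20 + 0.80 × 0.06 = 0.248, a difference of 0.032.
- Unadjusted SE = √[(0.280 × 0.720 + 0.248 × 0.752)/1000] = 0.0197.
- Adjusted SE ≈ √[0.80 × (0.10 × 0.90 + 0.06 × 0.94)/1000] = 0.0108.
- Power, from Φ(difference/SE - 1.96), is 37% unadjusted and 84% adjusted.

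| f | 10% vs 6%: unadjusted, adjusted | 20% vs 16%: unadjusted, adjusted |
|---|---|---|
| 5% | 73%, 90% | 54%, 62% |
| 10% | 57%, 88% | 45%, 60% |
| 20% | 37%, 84% | 33%, 55% |

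Simulation with robust SEs (4000 replicates, 10% vs 6%) gave 57.3% and 88.9% at f = 10%, and 36.6% and 84.0% at f = 20%. Type I error was 4.7% to 5.3%, with or without the covariate.

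**Step 3: does site adjustment already do the job?** If each hospital's ICU share followed its beds (75/604, 94/507, 15/233) and enrolment followed beds, site would explain under 2% of the variance in baseline ICU status. It does not stand in for the covariate.

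**Step 4: what adjustment does not change.** In the simulations the mean estimate was about 0.036 at f = 10% and 0.032 at f = 20%, adjusted or not. Both equal (1 - f) × 0.04. Adjustment removes noise and leaves the estimand alone.

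**The case against.** Adjusting only for stratification factors is a defensible, pre-specified choice, made in both documents. The outcome is secondary and has no power target. ICU enrolment is inferred from the absence of an exclusion, and the size of the loss rests on two assumed rates: at 5% in the ICU and 25% later ICU use, the gain is only 7%. All of this stands. It limits the importance of the point, but does not remove it, since the covariate costs nothing in bias or type I error.

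A reader might infer more than the documents support, in four ways:

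- **That the comparison is biased.** It is not. Randomization balances baseline ICU status on average, and type I error holds.
- **That the SAP departs from the protocol and should count only new admissions.** Section 5a refers to ICU admissions, but Aim 1 and Table 1 say ICU use, which the SAP's wording fits. The protocol's own terms differ from one another. Counting only new admissions in all patients would also score someone who stayed in the ICU for the full 30 days as 0.
- **That the shrunken effect is an error.** Under intention to treat, (1 - f) times the effect in the others is the valid average over everyone enrolled. Patients already in the ICU can still show benefit through ICU-free days.
- **That every patient in the ICU at randomization scores 1.** For someone leaving the ICU on the day of randomization, the score depends on whether that day counts, which the SAP does not say for this outcome.

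**Conclusion.** The point holds as a loss of precision. The plan leaves a strong, available baseline predictor out of the ICU-care models. Under the assumed ranges (5-25% in the ICU at randomization, 8-25% later ICU use among the others), including it would cut the standard error by about 7% to 49%, and by 35% at 15% and 10%. The actual gain depends on two rates that the documents do not give, and on ICU patients having been enrolled, which the eligibility text permits but does not state. There is no bias, and the primary outcome is unaffected. For ICU-free days a gain is plausible but was not computed. The change is worth making because it is cheap, but the trial's validity does not depend on it.

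**What to change.** 1. Add one pre-specified covariate, in ICU at randomization (yes/no), to the linear models for ICU care at 30 and 90 days, and to the ICU-free-day models. Amend the SAP's bar on other covariates to allow it.
2. Define it as an ICU stay that began before the randomization date and was still open on that date. The SAP ignores clock times, so this keeps transfers later on the randomization day from being treated as baseline. State whether ICU care on the randomization date itself counts towards the outcome.
3. Keep any ICU care as the outcome, and report the site-and-ADRD model as a sensitivity analysis. The SAP already mentions a data pull on 2/7/22. If outcome data have been unblinded, label the adjusted model supplementary.
4. In the reserve logistic model the covariate would predict the outcome almost perfectly, and its coefficient may not be estimable. Leave that model with site and ADRD only.
5. Optionally, add a supplementary analysis restricted to patients not in the ICU at randomization, which addresses the effect in those who can still avoid it. Do not replace the outcome with new admissions counted in all patients.
6. Reconcile the outcome's name across protocol section 5a, Aim 1, Table 1 and the SAP, stating whether a stay already under way counts.

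The cost is SAP wording and one variable derived from ICU dates that the SAP already uses. No new data collection is needed.

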Assessment of the implementation of the interventions in Aim 3 is guided by the RE-AIM Framework for implementation research³⁸⁻⁴¹ and the Consolidated Framework for Implementation Research (CFIR).⁴² RE-AIM is a multidimensional framework for evaluating the public health impact of efforts to translate research into practice.³⁹ The five dimensions of RE-AIM are reach of the intervention within the target population, effectiveness of the intervention, adoption by target staff members or settings, implementation consistency and quality, and maintenance of intervention delivery and effects.³⁸⁻⁴¹ CFIR is a pragmatic meta-theoretical framework that synthesizes constructs related to implementation of evidence-based interventions. The five overarching domains are intervention characteristics, outer setting, inner setting, characteristics of individuals, and process, and include a total of 37 constructs that can be used to understand what works, and why, in a certain setting.⁴² We collect quantitative and qualitative data on reach, effectiveness, adoption, implementation, and maintenance (RE-AIM) of the intervention. Quantitative data are collected as routine tracking as part of the implementation of both trials, with data on participation, intervention use, fidelity to the intervention, and changes over time (Table 2). Qualitative data are collected through short, semi-structured interviews (10-30 minutes) guided by the CFIR domains. The interviews are conducted in-person or by phone with patients (n=20) and family members (n=20) from Trial 2, and clinicians (n=50) from either Trial 1 or 2 after study involvement. All participants are selected using purposive sampling to ensure a diverse group based on level of participation, race, ethnicity, age, gender and, for clinicians, specialty, and year of training. A trained qualitative interviewer will interview participants using an interview guide, and interviews will be audio-recorded and transcribed.^{16,43-59.}

Table 1: Outcome measures and data collection

MAJOR OUTCOME MEASURES	CONCEPT	DATA COLLECTION: SOURCE & TIME
Aims 1 and 2 outcomes		
EHR documentation of goals-of-care discussion (Primary outcome for both Trials)	Goals-of-care discussion	EHR: 30 days post randomization
ICU use, ICU and hospital free days	Intensity of care	EHR: 30 days post randomization
7- and 30-day ICU and hospital readmissions	Intensity of care	EHR: 7 and 30 days following hospital discharge

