- EHR documentation of any hospital readmission within specified windows (7 days and 30 days) after discharge from the index hospitalization (excluding apparent readmissions that actually represented hospital transfers):  
Linear regression with robust standard errors; (logistic regression as additional analysis in case reviewers request it): outcome = 0 if no documentation of readmission during period of interest; 1 if readmission occurred during that period.
- Days out of the ICU and alive during specified periods (30 days and also 90 days) after randomization:  
Coding procedure:
  - Step 1: Compute the number of days alive during the period  
If patient died before the end of the period: number of days between randomization and death; If patient alive at the end of the period, number of days in period (30 or 90).
  - Step 2: Compute the number of days in the ICU during the period.
  - Step 3: Outcome measure = days alive minus days in the ICU.

Days-alive and days in ICU will be computed using only the DATES of randomization, death, and ICU admission and discharge. (Times will be ignored.)  
Primary analysis: Linear regression with robust standard errors (logistic regression as additional analysis in case reviewers request it)
- Days out of the hospital and alive during specified periods (30 days and also 90 days) after randomization:  
Coding procedure:
  - Step 1: Compute the number of days alive during the period  
If patient died before the end of the period: number of days between randomization and death; If patient alive at the end of the period, number of days in period (30 or 90).
  - Step 2: Compute the number of days in hospital during the period.
  - Step 3: Outcome measure = days alive minus days in hospital.

Days-alive and days in hospital will be computed using only the DATES of randomization, death, and ICU admission and discharge. (Times will be ignored.)  
Primary analysis: Linear regression with robust standard errors (logistic regression as additional analysis in case reviewers request it)

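### The SAP's hospital-free-days item lists ICU dates where its own steps need hospital admission and discharge dates

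*SAP*

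**What the plan says.** Under Secondary outcomes, the SAP derives days alive and out of hospital in three steps, for 30-day and 90-day windows. Step 1 counts days alive. The other two read "Step 2: Compute the number of days in hospital during the period" and "Step 3: Outcome measure = days alive minus days in hospital". The sentence after the steps fixes the data source: "Days-alive and days in hospital will be computed using only the DATES of randomization, death, and ICU admission and discharge". It adds that clock times are ignored.

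The item immediately before, days alive and out of the ICU, has the parallel sentence: "Days-alive and days in ICU will be computed using only the DATES of randomization, death, and ICU admission and discharge".

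Protocol section 5a treats the two as distinct measures: "ICU- and hospital-free days are defined as the number of days alive and outside of the ICU (or hospital) within the specified time period". Specific Aim 1 names both among its secondary outcomes ("Secondary outcomes focus on intensity of care: ICU use, ICU and hospital free days"), and Table 1 lists both ("ICU use, ICU and hospital free days").

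**The concern.** The data-source sentence is restrictive: it says these dates and no others. ICU dates cannot give the time a patient spends in hospital outside the ICU, which is what separates this outcome from ICU-free days. The sentence therefore contradicts the steps it is meant to implement, and no other part of either document lists hospital dates for this outcome.

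Hospital-free days is a named secondary outcome. Under the SAP's Additional analyses it is also carried into the ADRD interaction models, the separate ADRD and non-ADRD models, and the RE-AIM association tests. If the sentence were coded literally, the trial would report ICU-free days twice under two names, and ward time would drop out of this outcome altogether.

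**Working it through.** The plan gives no numerical figure for this outcome, so there is nothing to reproduce. The check compares the texts and then works through what the literal rule would do.

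**Comparing the texts.** The date sentences in the ICU and hospital items differ only in the outcome they name; the date list is identical. The list is right for the ICU item. For the hospital item it omits hospital admission and discharge.

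**Possible readings of the hospital item as written.**

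- (a) Days in hospital cannot be obtained from the listed dates, so no value can be computed.
- (b) ICU dates stand in for hospital dates, so the outcome equals ICU-free days.
- (c) 'Discharge' is taken to mean hospital discharge, and the count starts at randomization. This works for the index stay, because patients are inpatients at enrollment. It cannot count readmission days inside the window, which need hospital admission dates.

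**Per-patient effect under (b).** Let A be days alive in the window, I the ICU days, and R the remaining (ward) hospital days, so that hospital days = I + R.

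- Intended value: A − (I + R)
- Literal value: A − I
- Difference: R

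The stays below are assumed for illustration and are not trial data.

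| Assumed patient | I | R | Intended, 30 days | Literal, 30 days | Intended, 90 days | Literal, 90 days | Excess |
|---|---|---|---|---|---|---|---|
| Alive, ward only | 0 | 5 | 30 − 5 = 25 | 30 | 90 − 5 = 85 | 90 | 5 |
| Alive, ICU and ward | 4 | 6 | 30 − 10 = 20 | 26 | 90 − 10 = 80 | 86 | 6 |
| Alive, 10 index days plus 6 readmission days | 0 | 16 | 30 − 16 = 14 | 30 | 90 − 16 = 74 | 90 | 16 |
| Died in hospital on day 12, never in ICU | 0 | 12 | 12 − 12 = 0 | 12 | 12 − 12 = 0 | 12 | 12 |

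A patient with no ward days in the window (R = 0) is unaffected.

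Under (c), the third patient would score 30 − 10 = 20 at 30 days instead of 14, because the 6 readmission days are lost.

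**Between-arm effect under (b).** By definition, ICU-free days = hospital-free days + R. The SAP fits a linear regression on arm, hospital site and ADRD status, and least-squares coefficients on the same covariates add. Hence

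arm effect (literal) = arm effect (intended) + arm effect on R.

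The documents do not give the arm difference in R. If the intervention arm had 0, 0.5, 1 or 2 fewer ward days (assumed), the literal estimate would be lower than the intended one by 0, 0.5, 1 or 2 days.

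**The case against.** The strongest reply is that this is a clerical slip. The heading, Steps 2 and 3 and the protocol definition all define the outcome correctly. The faulty sentence mainly serves to say that calendar dates, not clock times, are used. A programmer would have to ignore the heading and two steps to reach reading (b), and a variable identical to the preceding one would be easy to spot. The ward stays and arm differences above are assumed, so they say nothing about this trial.

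Most of that stands, and it sets the weight of the point. The intent is clear, and nothing shows that the code is wrong. It does not remove the inconsistency, because the sentence is the SAP's only explicit data-source rule for this outcome and it limits itself to the dates listed. Reading 'discharge' as hospital discharge does not rescue it either: in the ICU item the same phrase means ICU discharge, and readmission days would still be missed.

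It can also be said that Step 2 already covers every stay in the period, so naming readmissions in the correction is not strictly needed. That is fair. Naming them simply rules out an index-stay-only count.

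**Conclusion.** The date list in the hospital-free-days item is wrong as written and conflicts with the item's own steps and with the protocol. The weight is minor. Read literally, the rule either gives no value or overstates each patient's hospital-free days by that patient's ward days (5 to 16 days in the assumed examples). The shift in the arm comparison would equal the arm difference in ward days, which the documents do not give and which could be zero. No bias is claimed. The documents do not show which dates the analysis code uses. The primary outcome, its significance level and the sample size are unaffected.

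**What to change.** In the hospital-free-days item, replace the reference to ICU dates with hospital admission and discharge dates, covering the index stay and any readmission within the window. Leave the ICU-free-days item as it is. Then confirm that the derivation code for the 30-day and 90-day variables reads hospital dates; comparing the hospital-free and ICU-free variables patient by patient would reveal a duplicate at once.

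The cost is one phrase in the SAP and one code check. No new data collection is evident: the SAP already relies on index discharge for a mortality time point ("death outcome measured from EHR data at time of index hospitalization discharge") and on readmissions after discharge for the readmission outcomes.
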